7.6.2 Serious Adverse Events and Adverse Event Leading to Discontinuation

Summaries of worst grade of on-study SAE, both by individual grade (1, 2, 3, 4, or 5, along with an Any Grade category) and by grade grouped as “Any, Grade 3-4 and Grade 5” will also be presented. These summaries will be repeated for:

- On-study drug-related SAEs
- On-study AEs leading to discontinuation.
- Drug related AEs leading to discontinuation

By-subject listings of SAEs and AEs leading to study drug discontinuation will be produced.

7.6.3 Safety by subgroups

Summaries of all adverse events with $\geq 5\%$ frequency, adverse events leading to discontinuation, serious adverse events (any grade, grade 3-4), and death within 60 days of last dose will be presented for the levels of the factors listed below.

In addition summaries by the same factors will be produced for SPM and infusion reaction.

- Age:

- < 65
- < 65 up to < 75
- ≥ 75 years
- Gender (male, female)
- Race
- Region (North America, European Union, and Rest of World)

7.6.4 Adverse Events of Special Interest

Infusion reaction is a known elotuzumab toxicity. It will be based on investigator assessment and will be defined as any non-serious or serious adverse event judged by the investigator to be infusion related and which also occurs on the day of or the day after the elotuzumab infusion. These summaries will be presented:

- Frequency tables of the worst grade of on-study investigator infusion reaction (any grade and grade 1 through 5) by treatment group. The same summary will be presented with grades grouped as Any, Grade 3-4 and Grade 5.
- Frequency of infusion reaction by infusion rate.
- Frequency of infusion reaction by cycle.

By-subject listings of infusion reactions will be produced.

Multiple myeloma is associated with immune dysfunction and the natural course of the disease includes increased infection risk. In addition, elotuzumab may inhibit some cellular components of the immune system. Therefore, a thorough characterization of infections will be presented. Infections will be based on the SOC ‘infections and infestations’ and opportunistic infections will be based on clinically pre-defined PT terms:

- Time to onset and duration of first infection
- Frequency of infections including opportunistic infections by treatment group.
- Absolute lymphocyte count at time of first infection
- Kinetics of lymphocyte reduction

7.6.5 Second Primary Malignancies

A summary table and a by-subject listing of second primary malignancies (SPM) will be provided. In addition, exposure-adjusted SPM incidence rates (including multiple occurrences of unique events) will be presented by treatment group and will be calculated as follows:

$$100 \times \left(\frac{\text{Total number of unique SPM events}}{\frac{\text{subject death date or last known alive date} - \text{subject date of first dose of study drug} + 1}{365.25}} \right)$$

Information on SPM will be obtained from the on-treatment eCRF page for secondary malignancies and the “Survival Status” eCRF page.

7.6.6 Deaths

The number and percentage of deaths and the investigator-reported cause of death will be presented, by treatment group and overall. This will be summarized for all deaths, and for those reported on study treatment or within 60 days of discontinuing study treatment.

7.6.7 Clinical Laboratory Evaluations

On-treatment laboratory tests for safety are defined as those that occur after first dose of any study therapy until 60 days after last dose of any study therapy.

The number and percentage of subjects with each worst severity grade for on-study hematology parameters (hemoglobin, WBC, ANC, ALC and platelets) will be presented, by treatment group. Grades will be categorized as Grade 1, Grade 2, Grade 3, Grade 4, Any Grade and Grade 3-4. Subjects will be counted only once for each parameter, according to their worst post baseline CTC grade. The percentage of subjects with each worst severity grade will be calculated out of the number of subjects with on-study assessment for each lab parameter. Subjects with no on treatment assessment for a lab parameter will be reported in the “Not Reported” category.

This summary will be repeated for:

- Liver parameters (ALT, AST, alkaline phosphatase, albumin and total bilirubin) with available CTC grades
- Renal/electrolyte parameters (sodium, potassium, bicarbonate, calcium, glucose and creatinine) with available CTC grades

Sodium, potassium, calcium, and glucose will be presented separately, based on their high and low values.

For blood urea nitrogen (BUN), direct bilirubin and total protein the worst category on-treatment will be presented. Results will be categorized as; below upper normal limits, above upper normal limits or not reported.

For reporting purposes, urea will be converted to BUN, using the conversion factor: urea (mmol/L) / 0.357 = BUN (mg/dL).

Subjects experiencing any potential drug induced liver injury (DILI) will be summarized by treatment group as follows:

- A summary of the number and percentage of subjects with (AST or ALT > 3 × upper limit of normal (ULN)) and (Total bilirubin > 2 × ULN and ALP < 2 × ULN) will be presented.

If any potential cases of DILI are identified then clinical review will be conducted to ensure no other immediate apparent possible causes of AT elevation and hyperbilirubinemia are present, including but not limited to, viral hepatitis, pre-existing chronic or acute liver disease, or the administration of other drugs known to be hepatotoxic.

Note: The timing for total bilirubin rising to >2xULN needs to be concomitant with or within 30 days after ALT or AST rising to >3xULN. ALP needs to be <2xULN at the time of or within 2 weeks before ALT or AST rising to > 3xULN or TBILI>2xULN. This means a normal ALP value (<= 2xULN) must be present within 2 weeks of either the ALT/AST criteria or the TBILI criteria.

A by subject listing of all laboratory data will be provided. A separate listing will be provided for all subjects potentially experiencing DILI.

7.6.8 *Electrocardiograms*

A by subject listing of electrocardiogram (ECG) data collected at screening will be presented.

7.6.9 *Vital Signs, Physical Measurements and Physical Examination*

Vital signs parameters (body temperature, respiratory rate, seated diastolic and systolic blood pressure and heart rate) will be presented by visit and time point in a subject listing.

[REDACTED]

8 CONVENTIONS

8.1 Baseline Definition

Baseline evaluations will be those performed within 60 days of randomization and prior to first dosing date. When an assessment is repeated multiple times within the screening period, the baseline evaluation will be the one closest to the first dosing date.

Laboratory tests and procedures (ECG, physical measurement and 2D echocardiogram MUGA, skeletal survey and plasmacytoma) done on the first date of dosing will be assumed to have occurred prior to dosing and therefore baseline evaluation for those parameters will be those prior or on the first dosing date.

8.2 Age Definition

Age (years) will be calculated as:

$$\frac{\text{date of informed consent} - \text{date of birth} + 1}{365.25}$$

8.3 Time Since Initial Diagnosis to Randomization Definition

Time from disease diagnosis to randomization (months) will be calculated as:

$$\frac{\text{date of randomization} - \text{date of initial diagnosis} + 1}{30.4375}$$

For the date of cancer diagnosis, the following conventions will be used for imputing partial dates:

- If only the day of the month is missing, the 15th of the month will be used to replace the missing day.
- If the day and month are missing or a date is completely missing, it will be considered as missing.

8.4 Duration and Study Day Definition

In instances in which study period between two dates are to be calculated (for example, duration of response, PFS and OS), the convention to be used is as follows: later date – earlier date + 1 day.

Study day is calculated as assessment date – first dose date + 1 day, if the assessment is taken on or after the first dose day. If the assessment is taken prior to the first dose day, study day will be calculated as assessment date – first dose date. Date of first dose is defined as Study Day 1.

8.5 Day Conversion of Date Imputation

Conversion from days to months or years:

- 1 year = 365.25 days
- 1 month = 30.4375 days

Imputation for partial or missing progression dates:

- If only the day is missing, the 1st of the month will be used to replace the missing day.
- If the day and month are missing or a date is completely missing, the date of progression will be moved back to the last complete tumor assessment date.

In both the cases given above, the imputed date will still be considered an event.

Imputation for partial or missing death dates:

- If only the day is missing, the later of the last known alive date and the 1st of the month will be used to replace the missing day.
- If both the day and the month are missing, the later of the last known alive date and Jan 1st will be used to replace the missing information.

In both the cases given above, the imputed date will still be considered an event.

For partial dates of start of subsequent anti-myeloma therapy, the following conventions will be used:

- When the day is missing, the alternative therapy will be assumed to start on the first day of the given month if this day is later than the last dosing date. Otherwise the alternative therapy will be assumed to start on the day following the last dosing date.
- When the day and the month are missing, the alternative therapy will be assumed to start on the first day of the given year if this day is later than the last dosing date. Otherwise the alternative therapy will be assumed to start on the day following the last dosing date.

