8 STATISTICAL CONSIDERATIONS

8.1 Sample Size Determination

The number of events and power for PFS were calculated assuming an exponential distribution in each arm. One interim analysis of PFS is planned. The comparisons of PFS will be carried out using log-rank tests stratified by stage of disease (International Staging System 1 - 2 versus 3), ECOG performance status (0 versus 1 - 2), and age (< 75 years old versus \geq 75 years old). The interim analysis will allow for early stopping for superiority. An O'Brien and Fleming α spending function will be employed to determine the stopping boundaries.

Approximately 750 subjects will be randomized to the 2 treatment groups in a 1 to 1 ratio in order to obtain at least 482 progression events, ie, documented progressions or deaths as determined by the IRC. Four hundred and eighty-two (482) events ensure that a two-sided, 5% level, sequential test procedure with 1 interim analysis after 70% of the total events (338) will have 90.5% power if the median PFS times in the control and experimental arms are 25 and 33.75 months, respectively, ie, if the hazard ratio of the experimental to control arm is 0.74. Assuming an accrual rate of 24 subjects per month, it will take approximately 60 months to obtain the required number of events, 31 months for accrual and 29 months for PFS follow-up. It is projected that at the time of final PFS analysis (at least 482 events), an observed hazard ratio of 0.84 or less, which corresponds to a 4.8 month or greater improvement in median PFS (25 vs 29.8 months), would result in a statistically significant improvement in PFS for the elotuzumab-containing arm. In view of evolving results with frontline lenalidomide therapy, a reassessment of the sample size could be made. The decision to reevaluate sample size would be based on external data only and would not involve a change in the required number of PFS events.

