4.1.1.3 Primary Definition of PFS

Primary Definition of PFS: PFS, under the primary definition, is the time from randomization to the date of the first documented tumor progression or to death due to any cause, provided progression or death does not occur more than 10 weeks (two or more assessment visits) after the last adequate tumor assessment. Clinical deterioration will not be considered progression.

The following censoring rules will be applied to the primary definition of PFS:

- Subjects who receive subsequent systemic anti-myeloma therapy prior to documented progression will be censored at the date of the last adequate tumor assessment prior to or on the initiation of the new therapy.
- Subjects who have an event (documented progression or death) > 10 weeks (2 assessment visits) after their last tumor assessment will be censored at their last adequate tumor assessment prior to the event.
- Subjects who neither receive subsequent therapy prior to progression nor have a progression event (including death) will be censored at their last adequate tumor assessment.
- In addition, subjects who do not have any post-baseline tumor assessments and who do not die within 10 weeks of randomization will be censored on the date of randomization.

In all cases, if there are no adequate assessments for censoring then the subject is censored on the date of randomization.

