7.2.2 Protocol Violations

A relevant protocol deviation is defined as a deviation from the protocol which is programmed in the database and which could potentially affect the interpretability of the study results.

The number and percentage of subjects with any relevant protocol deviation and each specific deviation will be presented overall and by treatment group.

The following eligibility deviations are considered relevant in this study and will be summarized for all randomized subjects:

1. Any prior systemic anti-myeloma therapy
2. Non-measurable disease. This occurs when none of the following three conditions are met:
 1. IgG, IgA, or IgM M-protein ≥ 0.5 g/dL
 2. Serum IgD M-protein ≥ 0.05 g/dL
 3. M-protein ≥ 200 mg in 24-hour urine.
3. No baseline tumor assessment. This occurs when there are no tumor assessments at all (laboratory assessments) on or prior to first day of dosing. See [section 4.1.1.1](#), for definition of adequate tumor assessment.

Also, the following on-treatment deviations are considered relevant in this study and will be summarized for all treated subjects:

4. Non-protocol specified systemic anti-myeloma therapy prior to discontinuation of study therapy
5. Received non-assigned treatment regimen throughout the study.

6. Subjects continuing to receive study therapy after 10 weeks of first documented progression per investigator (as progression should be confirmed).

If assessments based on the central laboratory is unavailable, but the local laboratory results are available, then those will be used for evaluating deviations 2 and 3.

A by subject listing of relevant protocol deviations will be provided.

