7.4.5 Subsequent Anti-Myeloma Therapies

The number and percentage of subjects with any subsequent systemic anti-myeloma therapy (2nd line), reason for first subsequent systemic anti-myeloma therapy regimen (Documented progression of disease, Clinical deterioration without documented progression, Maintenance therapy without disease progression or clinical deterioration, Consolidation without documented disease progression or clinical deterioration, or Other) and all subsequent systemic anti-myeloma therapy agents given categorized using the BMS WHO drug dictionary will be presented by treatment group.

The number and percentage of subjects with any second subsequent systemic anti-myeloma therapy (3rd line) and reason for second subsequent systemic anti-myeloma therapy regimen (Documented progression of disease, Clinical deterioration without documented progression, Maintenance therapy without disease progression or clinical deterioration, Consolidation without documented disease progression or clinical deterioration, or Other) will be presented by treatment group.

The number and percentage of subjects with any subsequent surgery, type of first subsequent surgery (Kyphoplasty, Orthopedic surgery, Debulking surgery or Other) will be presented by treatment group.

The number and percentage of subjects with any subsequent radiation therapy will be presented by treatment group.

A by-subject listing of all subsequent surgery, radiation therapy, and systemic anti-myeloma therapy will be provided.

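### SAP 8.5 dates partially recorded subsequent therapy without regard to the recorded month or to progression, so it can put the two in the wrong order for primary IRC PFS; the expected effect is small

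*SAP*

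**What the plan says.** SAP 8.5 gives two conventions for partial start dates of subsequent anti-myeloma therapy. With the day missing, the rule reads: "alternative therapy will be assumed to start on the first day of the given month if this day is later than the last dosing date". With day and month missing, 1 January of the recorded year takes the place of the first of the month. Both share one fallback: "Otherwise the alternative therapy will be assumed to start on the day following the last dosing date". Neither mentions the progression date, the reason for the therapy, or the end of the recorded month or year.

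The date matters because of SAP 4.1.1.3: "Subjects who receive subsequent systemic anti-myeloma therapy prior to documented progression will be censored at the date of the last adequate tumor assessment" on or before the start of that therapy.

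Four other provisions bear on it:
- Protocol 5.4.5.5 dates progression to the first of two consecutive qualifying values. Assessments are every 4 weeks and continue after study drug stops (Protocol 3.1, SAP 6.1).
- SAP 7.4.5 tabulates the "reason for first subsequent systemic anti-myeloma therapy regimen (Documented progression of disease" and further categories) and lists all subsequent therapy by subject.
- SAP 7.2.2 counts as a relevant deviation "Non-protocol specified systemic anti-myeloma therapy prior to discontinuation of study therapy" (deviation 4).
- SAP 7.5.5 states that the IRC has no data on subsequent therapy, so IRC review cannot correct the order of therapy and progression.

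**The concern.** The rule returns the later of two dates: the start of the recorded period, and the last dose plus one day. That goes wrong in two directions.

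**Too early.** A subject stops all study drug, later progresses, and then starts second-line therapy in the same month with the day not recorded. The first of that month precedes the progression, so a true event is censored at the last adequate assessment on or before the imputed date. Such censoring is informative, because it is applied to someone who did progress.

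**Too late.** A subject starts non-protocol therapy in one month while study dosing runs into a later one. The fallback moves the start out of its recorded month to after the last dose. A progression in between then counts as an event although the censoring rule excludes it.

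Both errors act on the definition used for the alpha-controlled test. The response analysis modified for subsequent therapy (SAP 7.5.5) depends on the same start date.

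**Working it through.** **1. The plan's own figure.** The documents give no figure for the imputation rule. The related design figure is that "a two-sided, 5% level, sequential test procedure with 1 interim analysis after 70% of the total events (338) will have 90.5% power" "if the hazard ratio of the experimental to control arm is 0.74", with 750 subjects randomized "in order to obtain at least 482 progression events". With O'Brien-Fleming-type spending at 70% information, the nominal levels come to 0.0148 and 0.0455, as SAP 2.5 states. Two-look power comes to 90.7%, against the stated 90.5%. The design reproduces.

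**2. The rule as a formula.** Let F be the first day of the recorded month (or year), L the last dose date and P the IRC progression date.

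Imputed start = F if F > L, otherwise L + 1. The subject is censored if the imputed start is before P.

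**3. Worked cases.**

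| Case | Last dose | Progression | True therapy start | Recorded | Imputed | Result |
|---|---|---|---|---|---|---|
| A | 20 Feb 2015 | 16 Mar 2015 | 25 Mar 2015 | month, year | 1 Mar 2015 | true event censored |
| B | 10 Dec 2014 | 15 Jun 2015 | 20 Jul 2015 | year | 1 Jan 2015 | true event censored |
| C | 10 Apr 2015 | 5 Apr 2015 | 12 Mar 2015 | month, year | 11 Apr 2015 | kept as event; should be censored |
| D | 20 Mar 2015 | 16 Mar 2015 | 25 Mar 2015 | month, year | 21 Mar 2015 | event, correct |

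Case D shows the protection. If the last dose is on, after, or one day before P, then L + 1 is not before P, and the first error cannot occur.

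**4. Error 1, exact enumeration.** Every day of 2014-2017 was taken as P, with the last dose 7 or more days earlier. Share with the imputed start before P:

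| Days from progression to therapy | 1 | 7 | 14 | 28 | 56 |
|---|---|---|---|---|---|
| Day missing | 93% | 74% | 51% | 5% | 0% |
| Year only | 99.5% | 98% | 96% | 92% | 84% |

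With the day missing, misordering requires P and the therapy start to share a calendar month, so the share falls quickly as the gap grows.

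**5. Error 1, with a spread of gaps.** Simulation of 200,000 progressors per setting. The last dose is 14-180 days before P. The gap to therapy is a fixed confirmation lag plus an exponential time with mean 10, 20 or 30 days (at least 1 day). The lags and means are assumptions; the documents give neither.

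| Confirmation lag | Day missing (mean 10 / 20 / 30) | Year only (mean 10 / 20 / 30) |
|---|---|---|
| none | 64% / 45% / 34% | 97% / 94% / 91% |
| 14 days | 24% / 14% / 10% | 93% / 90% / 88% |
| 28 days | 0.2% / 0.1% / 0.1% | 89% / 87% / 84% |

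**6. Error 2.** For every last-dose date in 2014-2017, therapy was started 0-119 days earlier with the day missing (1,461 × 120 = 175,320 cases). The imputed date fell on or before the last dose in none of them, and outside the recorded month in 88%.

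**7. What lost events would mean.** If events were lost at a fixed data cut, power would be 90.4% with 1% lost (477 events), 89.2% with 5% lost (458) and 87.6% with 10% lost (434). The analysis is triggered at 482 events, so losses would mainly delay it.

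**The case against.** The strongest reply concerns size, and most of it stands.

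- *Confirmation takes time.* Progression is dated to the first of two values, and scheduled assessments are 4 weeks apart. A sponsor that waits for the second scheduled value before changing therapy almost never meets error 1 with only the day missing. A reader might infer from the no-lag row that a third to two thirds of such events would be lost; the documents do not support that as the typical case. Nor is the share zero: the Protocol 5.1 tables allow confirmation after any interval, and not every criterion in 5.4.5.5 spells out a confirming test.
- *The exposed group is narrow.* It needs both a partial date and all study drug stopped at least two days before progression. The documents do not say how common partial dates are. A start known only to the year should be rare, since subjects off drug without progression are followed monthly and therapy start dates are collected.
- *Safeguards exist.* IRC PFS under the ITT definition does not censor for therapy and is a topline output, as are reverse Kaplan-Meier plots of censoring (SAP 8.7). The supportive PFS analyses are redacted, so further checks cannot be ruled out. Yet the ITT analysis is not the alpha-controlled test, and nothing visible requires a listing of the imputed dates that decide a subject's status.
- *Error 2 needs a departure from protocol*, because Protocol 3.1 and 3.5 require study treatment to stop once non-protocol therapy is given.

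Two further inferences go too far. One is that on-study rescue therapy would be hidden: all subsequent therapy is listed (SAP 7.4.5), and SAP 7.2.2 does not say that deviation 4 is derived from the imputed date. The other is that the hazard ratio is biased: that would need the errors to differ by arm, and nothing in the documents shows this.

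**Conclusion.** The flaw is real and lies in the literal rule: SAP 8.5 can return a date that contradicts the recorded month or year, and one that reverses the order of progression and therapy. Through SAP 4.1.1.3 it can censor a true event or keep one that should be censored. The two errors act in opposite directions on the event count.

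The conditional rates are those in steps 4 to 6 of the working. They rest on assumed gaps between progression and next therapy, and they apply only to subjects with partial dates who meet the stated conditions. Without the number of partial dates, neither the count of affected events nor the effect on the hazard ratio can be computed; for scale, each 1% of 482 events is about 5. The expected effect is small. The point merits correction because the rule feeds the primary analysis and costs little to repair.

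**What to change.** In SAP 8.5:

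(a) Always keep the imputed start inside the recorded month or year. If the last dose falls after that period, do not move the date past its end. Assess deviation 4 from the recorded month, not from the imputed date.

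(b) List every imputed start that decides whether a subject is a PFS event or censored.

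(c) Repeat the primary PFS analysis twice, with imputed starts set to the earliest and then to the latest date in the recorded period.

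Item (a) corrects the out-of-period dates. It does not remove error 1, because the first of the month lies inside the month; (b) and (c) make that error visible and bound it.

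The recorded reason for therapy should not drive the primary imputation. It is an investigator's entry in an open-label trial, and Protocol 5.4.1 recognises progression called on criteria outside the protocol. If only the year is known, therapy truly given before IRC progression could be moved after it, and a properly censored subject would become an event. Use the reason to place therapy after progression only when just the day is missing and the IRC progression date falls in that same month, and only as a sensitivity analysis.

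Cost: a few sentences in the SAP and minor programming. No new data are needed.
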